2.4.6 Study Update

To date, 28 patients have been enrolled on to this study, all of them have completed more than 1 cycle of treatment. The treatment of Rolapitant is well tolerated. In the first cohort- Cohort 1 (dexamethasone 12 mg on day 1, and 8 mg on days 2-5), none of the 9 patients had complete response in days 1-10. Since there is no interaction between Rolapitant and CYP3A4, the amendment 2 was written to keep the dose of dexamethasone constant at 12 mg on Days 2-5 for Part 1 (Rolapitant). In this new cohort- Cohort 2 (dexamethasone 12 mg on days 1-5), the complete response rate (no emetic episodes and no rescue medications) was 29% (5/19) in days 1-10; and the complete response rate was 32% (6/19) for emetic episodes only related to chemotherapy. We therefore would like to expand our experience with the current regimen to confirm the response rate prior to initiation of Part 2 of the study.

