5.0 Treatment Plan

5.1 Study Drug Treatment

This study will be conducted in 2 parts, part I and Part II, as follows:

Part I:

This part will be a single-arm phase II study of rolapitant administered as single-dose on Day 1. In this part, we will estimate the preliminary efficacy of rolapitant administered on day 1 by evaluating complete response (CR) in the single arm setting.

Up to 42 patients will be enrolled in part 1 (after the amendment 4) using the Simon's Minimax 2-stage design; 24 patients will be enrolled in the first stage. If \ge 2 out of 24 patients experience CR, additional 18 patients will be enrolled. The trial will be stopped early if less than 8 patients have complete response in nausea/vomiting.

With conclusion of Part 1 of study, communication of Part 1 study results will be presented to TerSera. In addition, publication of Part 1 study results may be presented for poster abstract and/or scientific journal for publication.

The decision to move on to Part II of this study will not depend on the results of the patients who have been treated with dexamethasone at 8 mg on Days 2-5. Rather, if the first part of the trial for the patients who will be treated with dexamethasone at 12 mg on Days 2-5 was not stopped early due to lack of efficacy of rolapitant and TerSera consents to continuation of the trial, the trial will proceed to the second part of the trial.

Treatment Plan:

All patients will receive anti-emetics approximately 1- 2 hrs prior to chemotherapy infusion as follow: Dexamethasone IV daily for 5 days (12 mg on days 1-5, after the amendment 2), Ondansetron (5HT3 receptor antagonist) 16 mg IV daily for 5 days as standard of care, and Rolapitant, 180 mg will be administered PO on Day 1. For 5-days Ifosfamide regimen, the anti-emetics will be given for 6 days.

Part II: This part will be a randomized, 2-arm phase II study of rolapitant vs fosaprepitant. If the trial was not stopped early, then the trial will proceed to the second part.

Assuming 40% and 11% CR rates in Arm A, and Arm B respectively, approximately 78 evaluable subjects will be randomly assigned to receive Rolapitant or fosaprepitant (1:1) administered as a single dose. The fosaprepitant arm will be used as standard arm to prevent patient selection bias.

Treatment Plan:

Patients will be randomized into two treatment arms: Arm A/ investigational arm: single dose of rolapitant n=39. Arm B/ control arm: single dose of fosaprepitant, n=39.

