11.0 Statistical Consideration and Sample Size

Statistical Considerations and Analysis

This is a phase II trial to study the treatment efficacy of rolapitant on nausea/vomiting in patients with sarcoma receiving multi-day chemotherapy with doxorubicin and ifosfamide regimen (AI). This trial will be carried out in two parts. The primary goal of the first part of the trial is to estimate the preliminary efficacy of rolapitant administered as single-dose on Day 1 by evaluating complete response (CR) rate in a single-arm setting. The primary objective of the second part of the trial is to establish the efficacy of rolapitant

administered as single-dose on Day 1 by evaluating CR rate in comparison with the efficacy of fosaprepitant administered as single-dose on Day 1.

Design and sample size/power

Part I: A single-arm phase II study of rolapitant administered as single-dose on Day 1

We will assess the efficacy of rolapitant on nausea/vomiting by evaluating CR rate using the Simon's Minimax 2-stage design (27). A patient will be considered as to have a CR if s/he does not experience chemotherapy related emesis and do not need rescue medication during cycle-1 following initiation chemotherapy. The primary endpoint is CR rate in cycle 1 (days 1-10). In our previous study, we observed 2 (11%) CRs among 18 patients who were treated with the standard of care. Based on the data of the 19 patients currently enrolled into this study, 6 out of 19 patients (32%) experienced CR. Therefore, a CR rate of 11% or less is considered as clinically insignificant, while a CR rate of 32% or higher is considered as clinically significant. When the probability of accepting an ineffective regimen (CR rate ≤ 11%) is 0.05 and the probability of rejecting an effective regimen (CR rate \geq 32%) is 0.05, the Simon Minimax 2-stage design requires 24 patients in the first stage. The drug will be rejected if no more than 2 responses are seen in the first stage. Otherwise, another 18 patients will be accrued. At the end of the trial, the drug will be rejected if no more than 8 responses are observed in a total of 42 evaluable patients (maximum accrual 47 patients; 42 evaluable, potential 10% drop out rate). The trial will be stopped early 50% of the time, and the mean sample size of the trial will be 33 if the true response rate is 11%. Accrual will be halted after the 24th patient is enrolled until 3 or more responses are seen in the first stage.

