Since there is no interaction between rolapitant and CYP3A4, the dose of dexamethasone will not be reduced from 12 mg to 8 mg and will be kept constant at 12 mg on Days 2-5 for Part 1 (Rolapitant), and Arm A (Rolapitant) of the Part 2 as stated in "Treatment Plan" section. After 9 patients were accrued to the first phase of Part I of the study with a dose of dexamethasone at 8 mg on Days 2-5, the protocol was amended to keep dexamethasone dose constant at 12 mg on Days 2-5. Up to date, 19 patients have been enrolled and treated with dexamethasone at 12 mg on Days 2-5 as a new cohort for the first stage of the Simon's Minimax 2-stage design, additional 5 patients will be accrued and treated in the first phase of Part I of the study as soon as this amendment is approved by IRB. The same rules of the design aforementioned will be applied.

Part II: A randomized, 2-arm phase II study of rolapitant vs fosaprepitant

The decision to move on to Part II of this study will not depend on the results of the patients who have been treated with dexamethasone at 8 mg on Days 2-5. Rather, if the first part of the trial for the patients who will be treated with dexamethasone at 12 mg on Days 2-5 was not stopped early due to lack of efficacy of rolapitant, the trial will proceed to the second part of the trial. This will be a randomized, 2-arm trial of rolapitant administered as single-dose on Day 1 in patients with sarcoma receiving multi-day

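### Sections 5.1 and 11.0 disagree on whether 8 complete responses in 42 reject rolapitant, and the Part II gate does not settle it

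*Combined protocol and SAP*

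**What the plan says.** Both sections describe one design for Part I: 24 patients, then 18 more, 42 in all.

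- **Stage 1.** Section 5.1 continues with at least "2 out of 24 patients experience CR, additional 18 patients will be enrolled". Section 11.0 says "The drug will be rejected if no more than 2 responses are seen in the first stage", and repeats the rule by holding accrual after the 24th patient until there are 3 or more responses.
- **Final count.** Section 5.1 says "The trial will be stopped early if less than 8 patients have complete response in nausea/vomiting", with no denominator. Section 11.0 says "the drug will be rejected if no more than 8 responses are observed in a total of 42 evaluable patients".
- **Operating characteristics.** Section 11.0 sets the null and target CR rates at 11% and 32%, with both error probabilities at 0.05. For a true rate of 11% it adds "The trial will be stopped early 50% of the time, and the mean sample size of the trial will be 33".
- **Gate to Part II.** Two sentences in Section 5.1 and one in Section 11.0 let Part II proceed if Part I was not stopped early. One of the Section 5.1 sentences also requires TerSera's consent. None mentions the 42-patient rejection rule.
- **Progress.** Section 11.0 records that "19 patients have been enrolled and treated with dexamethasone at 12 mg on Days 2-5 as a new cohort for the first stage", with 5 more to complete that stage, and that "6 out of 19 patients (32%) experienced CR".

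**The concern.** The two sections give opposite answers for 8 CRs in 42: Section 11.0 rejects the drug and Section 5.1 does not. Section 5.1 appears to have taken Simon's boundaries (2 and 8, the largest counts at which the drug is rejected) as the smallest counts at which it passes.

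The gate makes this worse. In Section 11.0, early stopping means the stage 1 stop, which occurs about half the time under the null. In Section 5.1 the same term is attached to the count of 8. Under the Section 11.0 usage, a drug that passes stage 1 and is then rejected at 42 patients was still not stopped early, so the gate reads as open.

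At stake are the go/no-go rule for Part I and entry to a randomised comparison illustrated at 78 patients. If the final count lands on 8, someone will have to choose the rule after seeing the result.

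**Working it through.** **Inputs.** From Section 11.0: null rate p0 = 0.11, target rate p1 = 0.32, n1 = 24, n2 = 18, rejection at 2 or fewer of 24 and at 8 or fewer of 42. From Section 5.1: continue at 2 or more of 24; stop below 8.

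**Assumption on the denominator.** I read the Section 5.1 count as out of 42. Read as out of 24, it would contradict that section's own rule of continuing at 2 or more. It would also stop a drug with a true 32% rate with probability P(X < 8 | 24, 0.32) = 0.479.

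**Formula.** If the trial continues at a or more of 24 and the drug passes at c or more of 42, then

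P(pass | p) = Σ over x from a to 24 of Bin(x; 24, p) × P(Bin(18, p) ≥ c − x).

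**Step 1: reproduce the stated design (a = 3, c = 9).** Early stopping at p0:

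0.89^24 + 24(0.11)(0.89^23) + 276(0.11²)(0.89^22) = 0.061 + 0.181 + 0.257 = 0.499.

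Mean sample size: 24 + 18 × (1 − 0.499) = 33.0. Both match Section 11.0. The type I error is 0.0358 and the power 0.9511. A full search over two-stage designs with these error limits finds no smaller total than 42. At 42, this design has the lowest expected size, so it is the minimax design.

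**Step 2: compare the cut-offs.**

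| Continue at / pass at | Type I error (p = 0.11) | Power (p = 0.32) | Early stop (p = 0.11) | Mean N (p = 0.11) |
|---|---|---|---|---|
| ≥3/24, ≥9/42 (Section 11.0) | 0.0358 | 0.951 | 0.499 | 33.0 |
| ≥2/24, ≥8/42 (Section 5.1) | 0.0841 | 0.979 | 0.242 | 37.6 |
| ≥3/24, ≥8/42 | 0.0815 | 0.976 | 0.499 | 33.0 |
| ≥2/24, ≥9/42 | 0.0363 | 0.953 | 0.242 | 37.6 |

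Nearly all the excess type I error comes from the final cut-off. These are properties of the rules as written, counted from the first patient.

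**Step 3: is 8 of 42 still reachable?** With 19 of 42 observed (all assumed evaluable), 23 remain. The CR definition for Part I in Section 11.0 counts chemotherapy-related emesis, which gives 6 of 19; Section 2.4.6 agrees: "the complete response rate was 32% (6/19) for emetic episodes only related to chemotherapy". Counting any emesis, Section 2.4.6 reports 5 of 19 (printed as 29%, although 5/19 is 26%; I use the count).

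- From 6 of 19, exactly 2 of 23 are needed. At 11% this is 253(0.11²)(0.89^21) = 0.265. At 20%, an assumed intermediate rate, it is 0.093; at 32%, 0.008.
- From 5 of 19, exactly 3 of 23 are needed. At 11% this is 1771(0.11³)(0.89^20) = 0.229. At 20% it is 0.163; at 32%, 0.026.

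With 5 or 6 CRs in hand, both stage 1 rules are already met. That mismatch can no longer change the course of the trial.

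**Step 4: the gate.** Since stage 1 is passed, any final count of 8 or fewer is literally not an early stop in the Section 11.0 sense. At a true rate of 11%, the chance of finishing there is 0.528 from 6 of 19 and 0.757 from 5 of 19. If the Section 5.1 count is taken as the final stop, counts below 8 are barred under that section and only exactly 8 stays open.

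**The case against.** The best defence is that Section 11.0 leaves little doubt about the intended design. It gives every parameter, states the stage 1 rule twice, gives the final rule with its denominator, and says the same rules apply to the current cohort. Section 5.1 is a treatment-plan summary. That tells a statistician which text is wrong. But no provision says which section prevails, and Section 5.1 is an operative part of the protocol.

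Second, the final rules differ at one outcome only, and other brakes exist. The Part I primary analysis is an estimate with an exact 95% confidence interval. Part II is to be sized from the observed Part I rate, and Table 1 starts at 30%, whereas 8/42 is 19% and 9/42 is 21%. TerSera must also consent. These points make an automatic run into Part II less likely, but none of them sets a boundary.

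Third, 0.036 against 0.084 compares the written designs, not the error left in the running trial. That is correct, and the figures should be read that way. It does not shrink the problem. Given 6 of 19 and a true rate of 11%, the chance of passing is 1 − 0.528 = 0.472 at 9 or more and 1 − 0.263 = 0.737 at 8 or more.

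**Conclusion.** The concern holds. The current text contains two decision rules for the same design, and only the Section 11.0 rule delivers the stated error rates, early-stopping probability and mean sample size. Under the Section 5.1 rule the type I error is 0.084, above the 0.05 limit, provided its count is out of 42. If another denominator was meant, the sentence is unclear and still needs correction.

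Exactly 8 of 42 remains a live outcome: 23% to 26% at a true rate of 11%, 9% to 16% at 20%, and 1% to 3% at 32%. The ranges span the two CR counts and assume that all 19 patients are evaluable. The outcome is most likely when the drug is no better than the null, which is when the rule matters most. The stage 1 mismatch is editorial by now. The gate wording is a separate gap, because it never refers to the final rejection rule.

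**What to change.** Five sentences change.

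- **Section 5.1, two cut-off sentences.** Continue only with at least 3 CRs in the first 24 patients. Reject the drug if 8 or fewer of 42 evaluable patients have a CR, so that at least 9 of 42 are needed. State the denominators.
- **Gate sentences, two in Section 5.1 and one in Section 11.0.** Part II opens only if Part I passed stage 1 and the drug was not rejected at the final analysis (at least 9 of 42). Keep TerSera's consent as the additional condition in Section 5.1.

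This restores the design already specified in Section 11.0 and needs no new patients, data or sample size calculation. It should be made before the final Part I count is known, so that the choice of rule cannot depend on the result.

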5.2 Chemotherapy

Al Regimen:

Ifosfamide: A total dose of 10 g/m² will be administered by IV bolus over 3 hours on days 1, 2, 3, 4 (2.5 g/m²/day); or on days 1, 2, 3, 4, 5 (2 g/m²/day).

Doxorubicin: 25 mg/m²/day IV continuous infusion for 72 hours on days 1, 2, and 3, completing infusion on day 4 (total dose: 75 mg/m^2).

Mesna: For Ifosfamide over 4 days: Prior to ifosfamide (Day 1) - 500 mg/m² (20% of ifosfamide dose) given simultaneously with ifosfamide and then daily continuous infusion (Days 1-4 completing infusion on day 4) – 1,500 mg/m²/day (60% of daily ifosfamide dose) for a total of 6 gm/m². For Ifosfamide over 5 days: Prior to ifosfamide (Day 1) - 400 mg/m² (20% of ifosfamide dose) given simultaneously with ifosfamide and then daily continuous infusion (Days 1-5 completing infusion on day 5) – 1,200 mg/m²/day (60% of daily ifosfamide dose) for a total of 6 gm/m². The mesna infusion will complete 24 hours after the last dose of ifosfamide.

Vincristine: 2 mg IV by rapid infusion (Day 1) may be given to the patients with sarcomas of small cell histology.

The chemotherapy cycles will be repeated around every 3 weeks if ANC > 1,500/mm³ and platelet count > 100,000/mm³ and the patient has recovered from any acute toxicities of chemotherapy.

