Arm A/ investigational arm: all patients (n=39) will receive anti-emetics approximately 1-2 hrs prior to chemotherapy infusion as follow: Dexamethasone IV daily for 5 days (12 mg on days 1-5), Ondansetron (5HT3 receptor antagonist) 16 mg IV daily for 5 days as standard of care, and Rolapitant, 180 mg will be administered PO on Day 1.

Arm B/control arm: all patients (n=39) will receive anti-emetics approximately 1- 2 hrs prior to chemotherapy infusion as follow: Dexamethasone IV daily for 5 days (12 mg on day 1, and 8 mg on days 2-5), Ondansetron (5HT3 receptor antagonist) 16 mg IV daily for 5 days as standard of care, and Fosaprepitant 150 mg will be administered IV on Day 1.

If patients don't achieve complete response to Fosaprepitant in cycle 1 in the control arm, they can be given 2 doses of fosaprepitant on days 1 and 4 in cycle 2.

Breakthrough nausea/vomiting and concomitant Medications

Patients may take the following agents for breakthrough nausea as needed: Ondansetron, Lorazepam, Diphenhydramine, and Promethazine.

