
For the analysis of the primary endpoint of the second part of the trial, Fisher exact test will be used to test the difference of CR rates between the two arms. CR rates along with their 95% confidence intervals (CIs) will be estimated by study arm. We will use logistic regression model (28) to assess the effect of patient specific covariates, such as treatment group, gender, etc. on the complete response. The secondary endpoints are the response rates in each of the time periods (0-24 hours, 24 hrs-120 hrs, and 120-240 hours). Logistic regression models using generalized estimating equations (GEE) will be

used to fit the response data to take the intra-patient correlation into account and to compare the differences of the response rates between the two treatment arms and to evaluate the effects of the patient specific covariates(29).

Toxicity data will be summarized by frequency tables for all patients and by treatment arm. For the efficacy endpoint, intent-to-treat analysis will be applied to the eligible patients. For the toxicity endpoint, per-treated analysis will be used to include any patient who received the treatment regardless of the eligibility nor the duration or dose of the treatment received.

If there are missing data, the reasons for missing data will be recorded, and missing-data mechanism will be checked. For data missing at random (MAR), multiple imputation techniques implemented in SAS PROC MI procedure to handle missing data will be used. For data missing not at random (MNAR), methods that add an explicit model for the missing mechanism to the data model will be applied.

The data from the patients who were treated with dexamethasone at 8 mg on Days 2-5 (prior to amendment 2) will be analyzed separately and included in relevant reports.

Randomization

Randomization will be carried out via CORe.

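### Part II does not fix the ifosfamide schedule (4 or 5 days) before a visibly different allocation is known; declaring it in CORe first and stratifying on it is a cheap safeguard

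*Combined protocol and SAP*

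**What the plan says.** Section 5.2 (Chemotherapy) gives the ifosfamide total as 10 g/m², delivered "on days 1, 2, 3, 4 (2.5 g/m²/day); or on days 1, 2, 3, 4, 5 (2 g/m²/day" basis. Doxorubicin is the same under both options. No section says which patients receive which schedule, who decides, or when. Section 5.2 adds that vincristine "may be given to the patients with sarcomas of small cell histology".

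For Part II, Section 5.1 states that "approximately 78 evaluable subjects will be randomly assigned to receive Rolapitant or fosaprepitant (1:1) administered as a single dose". In Arm A "Rolapitant, 180 mg will be administered PO on Day 1"; in Arm B "Fosaprepitant 150 mg will be administered IV on Day 1". No placebo or dummy is described, and blinding is not mentioned. The arms also differ in the dexamethasone dose on days 2-5. A cycle-2 option applies to one arm only, and its condition begins "If patients don't achieve complete response to Fosaprepitant in cycle 1 in the control arm".

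The Randomization paragraph of Section 11.0 is one sentence: "Randomization will be carried out via CORe". The Part II primary endpoint is CR over days 1-10 of cycle 1, compared by an unadjusted Fisher exact test. The supporting logistic and generalized estimating equations (GEE) models take patient covariates. Treatment group and gender are given as examples, and schedule is not named.

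The Part I treatment plan in Section 5.1 also says: "For 5-days Ifosfamide regimen, the anti-emetics will be given for 6 days". The Part II arm descriptions give 5 days only.

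**The concern.** The two schedules differ in daily ifosfamide dose (2.5 against 2 g/m²) and by one chemotherapy day, and both fall wholly inside the 10-day endpoint window. Section 2.1 describes delayed symptoms as lasting to about 120 hours after chemotherapy, so a day-5 infusion moves part of the at-risk period later within that window. The extra antiemetic day in the Part I plan suggests that the sponsor also regards schedule as relevant to emesis control.

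A co-treatment that may affect the outcome, is left to discretion and has no stated decision time can be chosen by someone who already knows the arm. The arms would then differ in something other than the antiemetic. Section 5.1 says the fosaprepitant arm is there to guard against selection bias, and this gap weakens that purpose.

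Later adjustment is not a full remedy. A schedule chosen after allocation is a post-randomisation variable, and conditioning on it does not restore the randomised comparison.

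**Working it through.** **Inputs from the documents (Sections 5.1 and 11.0).** 39 per arm, 1:1; CR 40% in Arm A and 11% in Arm B; Fisher exact test, two-sided 0.05; 80% power.

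**Inputs assumed.** CR by schedule and the share of patients on each schedule. The documents give neither, so ranges are shown.

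**1. The plan's own figure.** Summing the two binomial distributions over all tables that Fisher's test rejects gives power 80.2% at 39 per arm, and 39 is the smallest size that reaches 80%. The other Table 1 entries (78, 31, 24) also reproduce. The sample size is not in question.

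**2. Chance imbalance without stratification.** Let q be the true share on one schedule. The between-arm difference in share has SD = √(2q(1−q)/39).

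- q = 0.2: √(2 × 0.16/39) = 0.091
- q = 0.5: √(2 × 0.25/39) = 0.113

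Exact probabilities of a gap between two arms of 39:

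| q | 6 or more patients (15 points) | 8 or more patients (about 20 points) |
|---|---|---|
| 0.1 | 3.8% | 0.5% |
| 0.2 | 11.8% | 3.3% |
| 0.3 | 17.3% | 6.3% |
| 0.5 | 21.3% | 8.9% |

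The shift in the CR difference is the gap in shares times the CR difference between schedules. A 20-point gap with an assumed schedule effect of 10 to 20 points gives 0.20 × 0.10 = 2 to 0.20 × 0.20 = 4 points, against a planned difference of 40 − 11 = 29 points.

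**3. Selection after allocation, no drug effect.** If a share s of an arm is on the schedule with the lower CR, that arm's CR is high × (1 − s) + low × s. Example with CR 20% and 5% and shares of 30% in A and 70% in B:

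- Arm A: 0.20 × 0.7 + 0.05 × 0.3 = 15.5%
- Arm B: 0.20 × 0.3 + 0.05 × 0.7 = 9.5%
- False difference: 6 points

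Exact two-sided Fisher rejection at 39 per arm:

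| Assumed CR by schedule | 50/50 | 40/60 | 30/70 | 20/80 |
|---|---|---|---|---|
| 15% and 5% | 1.6% | 2.1% | 3.5% | 6.3% |
| 20% and 5% | 2.1% | 3.2% | 6.6% | 13.4% |
| 25% and 5% | 2.5% | 4.3% | 10.4% | 22.4% |

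The false difference is largest when the schedules separate completely by arm, and it then equals the schedule effect itself (15 points in the second row). A 40/60 split passes 5% only with a still larger effect: an assumed 40% and 11% by schedule, as large as the planned drug effect, gives 5.6%.

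**4. When the drug effect is real (40% and 11%).** A 4-point shift, split evenly between the arms, gives 38% and 13% with power 65%, or 42% and 9% with power 91%, depending on direction. Planned power is 80.2%.

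**The case against.** The strongest reply is that most of this is silence rather than error. No section says that the schedule is chosen after randomisation. The word open-label does not appear, although oral against intravenous dosing with no dummy, plus arm-specific dexamethasone, supports that reading strongly. A reader might infer that schedules will be steered by arm; the documents do not show it.

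Nor do they show that schedule changes CR. Total ifosfamide and doxorubicin are identical; one option has the higher daily dose and the other an extra day, so even the direction of any effect is unknown. The extra antiemetic day suggests relevance, but it also shows that the longer schedule was considered.

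A reader might also take the missing stratification as bias in itself. It is not: Fisher's test under randomisation already allows for chance imbalance, and many phase II trials of this size do not stratify. Nor is the possible bias open-ended, since it is capped by the schedule's own effect on CR.

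Vincristine is a weak example. Section 5.2 ties it to histology, a baseline trait, and Section 4.0 makes the indication for AI, or AI with vincristine, part of eligibility. Finally, schedule could be added to the planned logistic and GEE models as the plan stands.

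All of this stands, and it limits the point. What survives is narrower: nothing in the plan stops the schedule being settled after the arm is known, and a covariate recorded after allocation cannot undo that.

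**Conclusion.** This is a worthwhile, inexpensive improvement, not a flaw that invalidates Part II. The text supports three facts: a choice of schedule with no rule or decision time, arms that staff can tell apart, and no stratification factor. Together they leave open a route to bias that the plan could close.

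The size rests on assumed CR rates and shares. Chance imbalance is a matter of precision only. False-positive error passes 5% only with strong selection after allocation: with a 15-point schedule effect, 40/60 shares stay at 3.2%, while 30/70 and 20/80 reach 6.6% and 13.4%. The documents do not support the stronger conclusions that selection will occur, that the comparison is already biased, or that 39 per arm is wrong.

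Separately, the Part I and Part II text in Section 5.1 does not agree on the length of antiemetic cover with 5-day ifosfamide. It must be reconciled before Part II opens.

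**What to change.** In the Randomization paragraph of Section 11.0:

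- Require the intended cycle-1 ifosfamide schedule to be entered in CORe before the allocation is released.
- Stratify the 1:1 randomisation on that declared schedule (two levels).

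In Analysis Plans, name the declared schedule, not the schedule actually given, as a covariate in the logistic and GEE models. Keep the Fisher exact test as the primary analysis. Vincristine intent may be recorded at the same time but is not central.

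In Section 5.1, state for Part II how long antiemetics are given with 5-day ifosfamide, so that it agrees with the Part I text or explains the difference. No schedule or duration is preferred here.

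The cost is one CORe field, one two-level stratum, a few sentences in the protocol and slightly more randomisation set-up. The sample size stays at 39 per arm (exact power 80.2%). Section 2.4.6 indicates that Part II has not begun, so the change can be made in time.

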9.0 Criteria for Response

9.1 Response

All patients who receive one dose of study drugs (Rolapitant and fosaprepitant) under this protocol will be evaluable for response and toxicity.

9.2 The severity of nausea will be reported in patients diary using 4-point scale (Likert scale), as 0 (none), 1 (mild), 2 (moderate), and 3 (severe) during cycle-1 of chemotherapy.

9.3 Response will be defined as 0-24 hours, 24-120 hours, 120-240 hours, and overall period.

Complete response (CR): No emetic episodes and no rescue medications. **Complete control (CC):** CR and no more than mild nausea.

9.4 Toxicity: Toxicities will be graded using the Common Terminology Criteria for Adverse Events v4.03 – CTCAE (see Appendix C). Uncomplicated, severe, or life threatening neutropenia and thrombocytopenia are expected toxicities of the study chemotherapy regimen and as such will not be collected as adverse events in this study since the data is already captured through the PDMS/CORE.

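### Section 5.2 labels mesna as ending on day 4 or day 5, but its own 24-hour rule and 6 g/m² total put the end on day 5 or day 6

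*Combined protocol and SAP*

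**What the plan says.** Everything needed is in section 5.2 (Chemotherapy, AI regimen).

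- **Ifosfamide:** "by IV bolus over 3 hours on days 1, 2, 3, 4 (2.5 g/m²/day); or on days 1, 2, 3, 4, 5 (2 g/m²/day". The last dose is therefore on day 4 or day 5, depending on the schedule.
- **Mesna, 4-day schedule:** a day-1 dose of 500 mg/m², "given simultaneously with ifosfamide and then daily continuous infusion (Days 1-4 completing infusion on day 4", at 1,500 mg/m²/day.
- **Mesna, 5-day schedule:** a day-1 dose of 400 mg/m², "given simultaneously with ifosfamide and then daily continuous infusion (Days 1-5 completing infusion on day 5", at 1,200 mg/m²/day.
- **Mesna total, both schedules:** 6 g/m².
- **Closing rule:** "The mesna infusion will complete 24 hours after the last dose of ifosfamide".
- **Doxorubicin, same section:** "IV continuous infusion for 72 hours on days 1, 2, and 3, completing infusion on day 4".

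The section does not define a day and gives no start times.

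**The concern.** Each mesna label names the day of the last ifosfamide dose as the day on which the infusion stops, while the closing sentence requires the infusion to run for 24 hours beyond that dose. The two can agree only in a boundary case. The doxorubicin line adds to the doubt: a 72-hour infusion and a 96-hour infusion, both begun on day 1, are both labelled as ending on day 4.

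This is a working dosing instruction for the chemotherapy given in both parts and both arms, for up to six cycles (section 5.5). At stake is whether staff who read the label stop mesna before the protocol's own end point and below its own total.

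**Working it through.** **1. Reproduce the stated total.** The mesna fractions check: 20% of 2,500 and 2,000 mg/m² is 500 and 400; 60% is 1,500 and 1,200. Rate × days gives 1,500 × 4 = 6,000 mg/m² and 1,200 × 5 = 6,000 mg/m². The 6 g/m² is therefore the continuous infusion alone, without the day-1 dose.

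**2. Hours needed.** The hourly rates are 1,500/24 = 62.5 and 1,200/24 = 50 mg/m²/h. The durations are 6,000/62.5 = 96 h and 6,000/50 = 120 h.

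**3. Calendar days.** An infusion of 96 h from any clock time on day 1 ends at that clock time on day 5; 120 h ends on day 6. The 24-hour rule gives the same days: day 4 + 24 h = day 5 and day 5 + 24 h = day 6. With eight ifosfamide start times between 00:00 and 20:00, the end day was always 5 or 6, whether mesna began with or after the first ifosfamide dose, and whether the 24 hours ran from the start or the end of the last one.

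**4. Elapsed 24-hour days.** Count from the first ifosfamide dose, much as section 9.3 counts its response windows. Day 4 is then hours 72-96 and day 5 is hours 96-120. If the infusion follows the 3-hour ifosfamide, it starts at hour 3:

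| Schedule | End of infusion | Last ifosfamide ends | Plus 24 h | Falls in |
|---|---|---|---|---|
| 4-day | 3 + 96 = 99 | 72 + 3 = 75 | 99 | day 5 |
| 5-day | 3 + 120 = 123 | 96 + 3 = 99 | 123 | day 6 |

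In general the infusion ends at hour s + 96 or s + 120, where s is its start in hours into day 1. The labels need s = 0.

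**5. Shortfall if stopped at the end of the labelled day.** The infusion stops s hours early and is short by 62.5 × s (4-day) or 50 × s (5-day) mg/m². The documents do not give s, so these are illustrations:

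| Assumption | 4-day | 5-day |
|---|---|---|
| s = 0 | 0 | 0 |
| s = 3 (elapsed days, infusion starts when the first ifosfamide ends) | 187.5 mg/m²; 187.5/6,000 = 3.1% | 150 mg/m²; 2.5% |
| s = 11 (calendar days, ifosfamide at 08:00, infusion at 11:00, stop at midnight) | 687.5 mg/m²; 11.5% | 550 mg/m²; 9.2% |

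**6. Could the total include the day-1 dose?** The infusion would then last (6,000 − 500)/62.5 = 88 h or (6,000 − 400)/50 = 112 h. On calendar days, starting after a 3-hour ifosfamide dose, it would end on the labelled day only if ifosfamide began before about 05:00. Step 1 already rules this reading out, because rate × days gives exactly 6,000 without that dose.

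**The case against.** The best defence counts elapsed 24-hour days and starts the continuous infusion together with the first ifosfamide dose. It then runs to hour 96 (or 120), the end of day 4 (or day 5), with the full 6 g/m² given and 24 hours elapsed since the last dose began. Label, total and rule all agree. The wording leaves some room for this: the mesna sentence places the day-1 dose both before and together with ifosfamide, and the rule does not say whether the 24 hours run from the start or the end of the last dose. The doxorubicin line is not decisive either, since a 72-hour infusion begun any time after hour 0 also ends in an elapsed day 4. Finally, the paragraph states the total and the 24-hour rule outright, so staff would have to overlook both to underdose.

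Some of this stands. The zero-hour reading is possible, the text does not define a day, and every shortfall figure rests on an assumed start and stop. But the rescue needs three things at once: elapsed days, a continuous infusion starting at exactly hour 0 although the sentence puts it after the day-1 dose, and a 24-hour count from the start of the last dose. Relaxing the start time alone breaks it. From hour 3 to hour 96 is 93 h, and 93 × 62.5 = 5,812.5 mg/m², below the total; on the 5-day schedule, 117 × 50 = 5,850 mg/m². That the rule and total show the intended duration limits the harm, but it also shows that the labels are the part to correct.

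**Conclusion.** The concern holds. On ordinary day counting the two mesna labels contradict both the 24-hour rule and the 6 g/m² total, which agree with each other on day 5 (4-day schedule) and day 6 (5-day schedule). The labels survive only at the exact boundary s = 0. Section 5.1 extends anti-emetics to 6 days for 5-day ifosfamide, which is consistent with treatment reaching day 6 but does not prove it.

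The size of any underdose cannot be fixed from the documents. It is zero at s = 0 and grows by 62.5 or 50 mg/m² per hour of later start if mesna is stopped at the end of the labelled day. The error is confined to two labels and has no bearing on the endpoint, sample size, error rates or efficacy analysis. It should be corrected because it sits in an operative dosing instruction and could cut mesna short of the protocol's own requirement.

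**What to change.** Subject to sponsor confirmation, change two labels in the mesna paragraph of section 5.2. In the 4-day sentence, the infusion should be shown as completing on day 5; in the 5-day sentence, on day 6. Leave the doxorubicin label at day 4. The new labels remain sound even at s = 0, because hours 96 and 120 are the starts of day 5 and day 6.

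The cost is two words in one paragraph, with no change to the design or analysis.
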